## **10 STUDY DOCUMENTATION, CASE REPORT FORM AND RECORDS**

### **10.1 Source Data Verification**

Study monitors will perform ongoing source document verification to confirm that critical protocol data (ie, source data) entered into the CRFs by authorized site personnel are accurate, complete, and verifiable from source documents.

Source documents include, but are not limited to, hospital records, clinical and office charts, laboratory notes, memoranda, patient diaries or evaluation checklists, pharmacy dispensing records, recorded data from automated instruments, copies of transcriptions that are certified after verification as being accurate and complete, microfiche, photographic negatives, microfilm or magnetic media, X-rays, patient files, and records kept at the pharmacy, laboratories, and medico-technical departments involved in a clinical trial.

Source documents that are required to verify the validity and completeness of data entered into the CRFs must never be obliterated or destroyed.

To facilitate source document verification, the investigator(s) and institution(s) must provide the sponsor direct access to applicable source documents and reports for trial-related monitoring, sponsor audits, and IEC/IRB review. The investigational site must also allow inspection by applicable regulatory authorities.

### **10.2 Use of Computerized System**

When clinical observations are entered directly into an investigational site's computerized medical record system (i.e., in lieu of original hardcopy records), the electronic record can serve as the source document if the system has been validated in accordance with FDA requirements pertaining to computerized systems used in clinical research. An acceptable computerized data collection system (for clinical research purposes) would be one that (1) allows data entry only by authorized individuals; (2) prevents the deletion or alteration of previously entered data and provides an audit trail for such data changes (eg, modification of file); (3) protects the database from tampering; and (4) ensures data preservation.

If a site's computerized medical record system is not adequately validated for the purposes of clinical research (as opposed to general clinical practice), applicable hardcopy source documents must be maintained to ensure that critical protocol data entered into the CRFs can be verified.

### **10.3 Retention of Records**

US FDA regulations (21 CFR §312.62[c]) and the ICH Guideline for Good Clinical Practice (GCP) require that records and documents pertaining to the conduct of this study and the distribution of investigational drug, including CRFs, consent forms, laboratory test results, and medication inventory records, must be retained by the Principal Investigator for 2 years after the last marketing application approval in an ICH region or after at least 2 years have elapsed since formal discontinuation of clinical development of the investigational product. All state and local laws for retention of records also apply. No records should be disposed of without the written approval of Hutchison MediPharma. Written notification should be provided to Hutchison MediPharma for transfer of any records to another party or moving them to another location.

## 11 MONITORING

It is understood that the responsible Hutchison MediPharma monitor (or designee) will contact and visit the investigator regularly and will be allowed, on request, to inspect the various records of the trial (CRFs and other pertinent data) provided that patient confidentiality is maintained in accord with local requirements.

It will be the monitor's responsibility to inspect the CRFs at regular intervals throughout the study and to verify the adherence to the protocol and the completeness, consistency, and accuracy of the data being entered on them. The monitor should have access to laboratory test reports and other patient records needed to verify the entries on the CRF. The investigator (or deputy) agrees to cooperate with the monitor to ensure that any problems detected during these monitoring visits are resolved.

## 12 DATA QUALITY

The overall procedures for quality assurance of clinical study data are described in the sponsor or designee Standard Operational Procedures.

Accurate and reliable data collection will be assured by verification and cross-check of the CRFs against the investigator's records by the study monitor (source document verification], and the maintenance of a drug-dispensing log by the investigator.

The sponsor or its agent will be responsible for data management of this study according to data management documents. Any decision to use the CRF as a source document must be stated in the Data Validation Manual and the investigator must be advised of this decision. A comprehensive validation check program will verify the data and discrepancy will be generated accordingly. In the event of discrepant data, the sponsor or its agent will issue data queries to the site and request data clarification. Site is required to respond to all queries and promptly enter data into the EDC system.

The CRFs and correction documentation will be maintained in the EDC system's audit trail. System backups for data stored by the sponsor and records retention for the study data will be consistent with the sponsor's standard procedures.

In order to facilitate analysis of the biological samples collected in this study, the treatment code will be released to the responsible analytical person when the samples have been received at the analytical site and are ready for assay. The result of the analysis must not be released with individual identification of the patient until the database is closed.

### 12.1 Assignment of Preferred Terms and Original Terminology

For classification purposes, preferred terms will be assigned to the original terms entered in the CRF, using the most up to date version of MedDRA for AEs and diseases and World Health Organization (WHO) drug terms and procedures dictionary for treatments and surgical and medical procedures.

## **13 USE OF INFORMATION AND PUBLICATION**

### **13.1 Use of Information**

All information regarding fruquintinib and Hutchison MediPharma's operations, such as Hutchison MediPharma's patent applications, formulae, manufacturing processes, basic scientific data, or formulation information, supplied by Hutchison MediPharma and not previously published is considered confidential information.

The information developed during the conduct of this clinical study is also considered confidential and will be used by Hutchison MediPharma in connection with the development of fruquintinib. This information may be disclosed as deemed necessary by Hutchison MediPharma or its designee to other clinical investigators, other pharmaceutical companies, and to the regulatory agencies. To allow for the use of the information derived from this clinical study and to ensure complete and thorough analysis, the investigator is obligated to provide Hutchison MediPharma with complete test results and all data developed in this study and to provide direct access to source data/documents for trial-related monitoring, audits, IEC/IRB review, and regulatory inspection.

The investigator will maintain a confidential patient identification code list of all patients enrolled in the study (by name and patient number). This list will be maintained at the site and will not be retrieved by Hutchison MediPharma or its designee.

### **13.2 Publication**

Core publication(s) will be authored by specified principal investigator(s) who contribute significantly to the implementation and conduct of the study and non-site personnel who contribute substantially to the design, interpretation, or analysis of the study (eg, Hutchison MediPharma or consultants). Hutchison MediPharma scientists making significant contributions to the study will be included in the list of authors. Hutchison MediPharma agrees that before it publishes any results of this study, it shall provide the investigator a pre-publication manuscript for review at least 30 days prior to the submission of the manuscript to the publisher.

The investigators have the right to publish the results of the study, but with due regard to the protection of confidential information. Accordingly, Hutchison MediPharma shall have the right to review and approve any paper for publication, including oral presentation and abstracts, which utilize data generated from this study. At least 30 days before any such paper or abstract is presented or submitted for publication, a complete copy shall be given to Hutchison MediPharma for review. Hutchison MediPharma shall review any such paper or abstract and give its comments to the author(s) promptly. The investigator shall comply with Hutchison MediPharma's confidential information in any such paper and agrees to withhold publication of the same for an additional 30 days in order to permit Hutchison MediPharma to obtain patent or other proprietary rights protection, if Hutchison MediPharma deems it necessary.

This confidential information shall remain the sole property of Hutchison MediPharma, shall not be disclosed to others without the written consent of Hutchison MediPharma, and shall not be used except in the performance of this study.

It is understood by the investigator that the information developed in the clinical study will

be used by Hutchison MediPharma in connection with the development of fruquintinib and, therefore, may be disclosed as required to other clinical investigators, other pharmaceutical companies, or to regulatory agencies. It is understood that there is an obligation to provide Hutchison MediPharma with complete test results and all data resulting from this study and to provide direct access to source data/documents for study related monitoring, audits, IEC/IRB review, and regulatory inspection.

**Appendix A Study Schedule of Events**

Date Procedure	Treatment 											Treatment Completion 	Follow-up
	Screening		Cycle 1				Cycle 2-3		Cycle 4 and onwards				
	Day -28 to Day -1	Day -7 to Day -1	Day 1	Day 8 (±1d)	Day 15 (±1d)	Day 22 (±1d)	Day 1 (±3d)	Day 15 (±3d)	Day 1 of each subsequent cycle (±3d)				
Informed consent 	X												
Tumor assessment (Dose Escalation, Expansion Cohorts C, D, E)	X		Screening, then every 8 (±1) weeks thereafter ( eg C3D1, C5D1, C7D1, etc.)								X 		
Tumor assessment (Dose Expansion Cohorts A and B only)	X		Screening, C2D1, C3D1 C4D1, and every 8 (±1) weeks thereafter (eg C6D1, C8D1, C10D1, etc.)								X 		
Medical history, demographics	X												
Concomitant medication 	X	X	X	X	X	X	X	X	X	X	X	X	
ECOG performance status		X	X		X		X	X	X	X	X	X	
Vital signs 		X	X	X	X	X	X	X	X	X	X	X	
Complete physical examination 		X											
Limited physical examination 			X	X	X	X	X	X	X	X	X	X	
Height	X												
Hematology 		X		X	X	X	X	X	X	X	X	X	

Date Procedure	Screening		Treatment 							Treatment Completion 	Follow-up
			Cycle 1				Cycle 2-3		Cycle 4 and onwards		
	Day -28 to Day -1	Day -7 to Day -1	Day 1	Day 8 (±1d)	Day 15 (±1d)	Day 22 (±1d)	Day 1 (±3d)	Day 15 (±3d)	Day 1 of each subsequent cycle (±3d)	30 (±7) days after permanent treatment discontinuation	Every 12 (±2) weeks from Treatment Completion Visit
Coagulation assay (aPTT, INR)		X		X	X	X	X	X	X	X	
Chemistry panel 		X		X	X	X	X	X	X	X	
Urinalysis 		X		X	X	X	X	X	X	X	
Echocardiogram 	X		X (Every 12 weeks ± 1 week after the first dose)							X	
Thyroid function test 	X						X		X	X	
Serum pregnancy tests 		X								X	
Urine pregnancy tests 							X		X		
Specific tumor markers  Dose Escalation, Expansion Cohorts C, D, E)	X		Screening, then every 8 (±1) weeks thereafter: C3D1, C5D1, C7D1, etc								
Specific tumor markers  Dose Expansion Cohorts A and B only)			Screening, C2D1, C3D1 C4D1, and every 8 (±1) weeks thereafter								
12-lead electrocardiogram 		X	X		X		X		X	X	
PK plasma sampling			PK samples are being collected on Days 1, 2, 14, and 15 of Cycle 1 for Expansion Cohorts B, C, D, and E. Refer to Appendix D for								

Date Procedure	Screening		Treatment 							Treatment Completion 	Follow-up
			Cycle 1				Cycle 2-3		Cycle 4 and onwards		
	Day -28 to Day -1	Day -7 to Day -1	Day 1	Day 8 (±1d)	Day 15 (±1d)	Day 22 (±1d)	Day 1 (±3d)	Day 15 (±3d)	Day 1 of each subsequent cycle (±3d)	30 (±7) days after permanent treatment discontinuation	Every 12 (±2) weeks from Treatment Completion Visit
			specific timepoints								
Adverse event 	X	X	X	X	X	X	X	X	X	X	
Fruquintinib treatment			Once daily, 3 weeks on/ 1 week off								
Survival follow up 											X

Note:

1. A written informed consent form should be obtained prior to any protocol-specific procedure or test. Tests completed within 28 days prior to enrollment can be used for screening and do not need to be repeated (except hematology, coagulation test, clinical chemistry, or urinalysis results).
2. Unless otherwise indicated, the visit window during the treatment period will be ± 3 days (± 1 day during cycle 1).
3. Patients who complete or prematurely discontinue the study need to return to the study site for a follow-up at 30 (±7) days after the decision to discontinue treatment permanently. Ongoing AEs will be followed until the event has resolved to baseline grade, the event is assessed as stable by the investigator, new anti-tumor treatment is initiated, the patient is lost to follow-up, the patient withdraws consent, or when it has been determined that the study treatment or participation is not the cause of the AE.
4. The treatment completion visit tumor assessment can be omitted if treatment ended because of disease progression or the patient had a tumor assessment within 14 days prior to the last dose of study drug.
5. Concomitant medication includes any prescribed or over-the-counter medicines. All medication used by patients within 7 days before screening and 30 days after study treatment completion should be recorded. At each visit, all medication used since the prior visit should be recorded.

6. Vital signs include blood pressure, heart rate, respiratory rate, and temperature. For patient with a baseline history of antihypertensive medications, blood pressure should be monitored at 3 hours ( $\pm 2$  hours) after the daily doses of anti-hypertensive medication.
7. Please refer to Section 6.3.2 for the assessments that should be completed as part of the Complete and Limited Physical Exams.
8. Hematology consists of complete blood count, including red blood cell count, hemoglobin, hematocrit, reticulocyte count, white blood cell count with differential (neutrophils, bands, lymphocytes, eosinophils, monocytes, basophils, and other cells), and platelet count.
9. The chemistry panel includes blood urea nitrogen, creatinine and creatinine clearance, sodium, potassium, chlorine, bicarbonate, calcium, magnesium, phosphorus, glucose, alanine aminotransferase, bilirubin (total), aspartate aminotransferase, alkaline phosphatase, lactate dehydrogenase, total cholesterol, triglycerides, uric acid, protein (total) and albumin.
10. Urinalysis includes pH, glucose, protein, and blood. A 24-hour urine should be collected from all patients with  $>1+$  proteinuria for quantitative test of urine protein during the screening. If protein  $\geq 2+$  during the period of study treatment, a 24-hour urine test should be conducted within 1 week.
11. MUGAs are permitted if echocardiograms cannot be performed.
12. Includes free T3, free T4, and thyroid-stimulating hormone (TSH).
13. Women of childbearing potential will receive a serum pregnancy test during screening and within 30 days after treatment completion, and a urine pregnancy test on Day 1 of each 28-day cycle beginning at Cycle 2. If pregnancy is suspected, additional tests should be completed. In the case of menopausal women, the date of menopause onset should be recorded.
14. CA125 level for patients with ovarian cancer, PSA for patients with prostate cancer, or other tumor markers (as appropriate) should be obtained as clinically indicated or with each tumor assessment.
15. On Days 1 and 15 in Cycle 1, ECG should be performed at pre-dose and at 3 hours ( $\pm 15$  minutes) post-dose (around  $C_{max}$  after single dose and at steady state in order to evaluate concentration-QT relationship for fruquintinib). Untimed ECG will be conducted on Day 1 of each cycle from Cycle 2 and onward.
16. After informed consent, all SAEs and concomitant medications will be collected. After initiation of study drug, all AEs and SAEs will be collected until 30 days following the last dose of study drug or a new treatment of anti-tumor therapy, whichever is earlier. After this period, investigators should report only SAEs that are considered to be related to the study drug.

17. **For subjects in Expansion Cohorts B, C, D, and E** - Survival follow-up (by telephone) should be performed every 12 ( $\pm$ 2) weeks from the date of the Treatment Completion visit. All subsequent anti-tumor therapy and information about ongoing or unresolved study drug-related SAEs will be collected. For the patients that discontinue the study without PD, all available tumor assessment results during survival follow-up will be recorded in the CRF until confirmation of PD. The date and cause of death should be recorded, if applicable. Patients who withdraw consent are encouraged to be followed for survival. If the patient has clearly expressed his/her refusal to be followed after withdrawal of consent, he/she will terminate the study and no survival follow-up will be performed.

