**Table 11 Dose Modification for Hypertension**

AE Grading and Definitions	Dose adjustment	Treatment Suggestions
Grade 1: prehypertension  (systolic BP 120-139 mmHg or diastolic BP 80-89 mmHg)	None	Follow up as planned schedule
Grade 2: SBP 140-159 mmHg or DBP of 90-99 mmHg; or DBP symptomatic increase >20 mmHg	None	Treatment objective: lower the blood pressure to <140/90 mmHg (or <130/80 mmHg in patients with chronic renal disease and/or diabetes).  Refer to Appendix I .
Grade 3: SBP $\geq$ 160 mmHg or DBP $\geq$ 100mmHg; or more than one drug or more intensive therapy are used	Interrupted once Grade3 hypertension lasting more than 7 days after using or adjusting antihypertensive drug; Should the BP of the patient recover to Grade 1 or the baseline level, one time of dose reduction shall be made.	Treatment objective: lower the blood pressure to <140/90 mmHg (or <130/80 mmHg in patients with chronic renal disease and/or diabetes).  Refer to Appendix I .
Grade 4: Life threatening (eg, malignant hypertension, temporary or permanent neurological deficits and hypertensive crisis)	The drug should be terminated.	Emergent medical treatment.

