### 6.2 Assessments During Treatment Phase

All visits must occur within  $\pm 3$  days ( $\pm 1$  day during cycle 1) from the scheduled date, unless otherwise noted (see [Appendix A](#)). All assessments will be performed on the day of the specified visit unless a time window is specified. Please see the Study Flowchart provided in [Appendix A](#) for the schedule of treatment period assessments.

If scheduled study assessments cannot be obtained because of a holiday, assessments during Cycle 1 should be done either prior to or immediately after the schedule interruption, regardless of the proximity to the next scheduled visits. If assessments cannot be obtained due to a holiday for any other cycle, these assessments should be obtained at the soonest following date, unless the soonest following date is within 7 days of other, regularly scheduled study assessments.

If during the DLT assessment window, 2 or more patients in a single cohort experience the same study drug-related Grade 3 toxicity that does not otherwise qualify as a DLT, the patients subsequently enrolled to this dose level and to the subsequent dose level will undergo increased monitoring during Cycle 1, as clinically indicated. Note: DLTs will not be collected during the Dose Expansion Phase.

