### 6.3 Safety Assessments

#### 6.3.1 Vital Signs Assessment

Vital signs will include measurements of body temperature, heart rate, respiratory rate, and systolic and diastolic blood pressure while the patient is in a seated position. The patient should be seated for approximately 5 minutes before the measurement of the blood pressure. For patients with a baseline history of hypertension, or those who develop hypertension during the study, blood pressure should be monitored daily by the patient at home, at

3 hours ( $\pm 2$  hours) after the daily doses of anti-hypertensive medication, and the results recorded in a blood pressure diary. Patients monitoring their blood pressure should bring their diary to each study visit.

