43	
Page 46, Section 5.3.1 Concomitant Therapies, 1st paragraph.
	
Page 46, Section 5.3.1 Concomitant Therapies, 1st paragraph.
 
The investigator should closely monitor patients receiving anti-platelet and/or anti-thrombotic drugs with INR, aPTT and platelet count during study drug treatment and make a timely decision on whether to continue or stop such drugs in patients that report Grade <math>\geq 2</math> hemorrhagic events at any site, based on an individual assessment of the risk-benefit balance (See Appendix J for additional information on the clinical management of severe or serious hemorrhagic AEs).
	
This paragraph was added to instruct investigators to closely monitor coagulation-related lab results and consider whether anti-platelet and/or anti-thrombotic concomitant medications should be continued in the event of Grade <math>\geq 2</math> hemorrhagic events at any site. This is designed to mitigate the risk of severe (Grade <math>\geq 3</math>) and serious (SAEs) hemorrhagic AEs

44	
Page 47, Section 6.1, Safety Assessments, Vital Signs Assessment, 1st paragraph, 3rd sentence.
 
For patients with a baseline history of antihypertensive medications, blood pressure should be monitored at 3 hours (<math>\pm 2</math> hours) after the daily doses of anti-hypertensive medication.
	
Page 47, Section 6.1, Safety Assessments, Vital Signs Assessment, 1st paragraph, 3rd sentence.
 
For patients with a baseline history of hypertension, or those who develop hypertension during the study, blood pressure should be monitored daily by the patient at home, at 3 hours (<math>\pm 2</math> hours) after the daily doses of anti-hypertensive medication, and the results recorded in a blood pressure diary. Patients monitoring their blood pressure should bring their
	
Clarification that patients with hypertension must monitor their blood pressure at home and keep a diary of the results.

	Prior version: v1.1	Current version: v2.0	Reason for Amendment
		diary to each study visit.	

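### Section 6.3.1 and Appendix A footnote 6 do not match on which patients have extra blood-pressure monitoring, how often, and how it is recorded

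*Protocol*

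**What the plan says.** Protocol Section 6.3.1 defines two groups for extra blood-pressure monitoring. The first is given as "For patients with a baseline history of hypertension". The second follows directly: "or those who develop hypertension during the study, blood pressure should be monitored daily by the patient at home". The readings are taken 3 hours (±2 hours) after antihypertensive dosing, with "the results recorded in a blood pressure diary", and the diary comes to every study visit.

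Footnote 6 of Appendix A covers the same subject. It opens with "Vital signs include blood pressure, heart rate, respiratory rate, and temperature", and the schedule marks vital signs at each treatment visit for all patients. It then says "For patient with a baseline history of antihypertensive medications, blood pressure should be monitored at 3 hours", with the same ±2-hour window. It goes no further. SAP Appendix 1 reprints the footnote unchanged.

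Two other places bear on the point. Section 6.2 refers sites to Appendix A "for the schedule of treatment period assessments". Table 11, on dose modification for hypertension, ties its Grade 3 action to duration: "Interrupted once Grade3 hypertension lasting more than 7 days after using or adjusting antihypertensive drug".

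**The concern.** Two current passages of one protocol give different instructions for the same safety measurement. The narrower instruction sits in the schedule that sites are told to work from. Footnote 7 of that schedule refers the reader to Section 6.3.2 for the physical examination, but footnote 6 has no such reference to Section 6.3.1. It therefore reads as complete.

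The group left out of footnote 6 matters clinically. Exclusion criterion 8 bars patients with systolic pressure of 140 mmHg or more, or diastolic pressure of 90 mmHg or more. Pressures in the Grade 2 and Grade 3 ranges of Table 11 would therefore largely first appear on study. Patients in whom that happens, and who have no history of antihypertensive medication, are named in 6.3.1 and not in footnote 6. At stake is whether the daily readings and diary exist when a dosing decision depends on how long raised pressure has lasted, and whether sites collect them alike.

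**Working it through.** The plan has no figure to reproduce on this point. The check compares the two texts and then the visit spacing.

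**1. The two instructions side by side**

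| Item | Section 6.3.1 | Appendix A footnote 6 (and SAP Appendix 1) |
|---|---|---|
| Baseline group | History of hypertension | History of antihypertensive medication |
| On-study group | Patients who develop hypertension | Not named |
| Time after dosing | 3 hours (±2 hours) | 3 hours (±2 hours) |
| Frequency | Daily | Not stated |
| Place | Home, by the patient | Not stated |
| Record | Diary, brought to each visit | Not stated |

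The timing agrees and the other items do not. Even the baseline groups differ, since one is defined by the condition and the other by medication. For the baseline group too, footnote 6 omits the home readings and the diary.

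**2. Where the difference probably came from**

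The Amendment 2 log describes superseded text, so a difference from it is not itself an error, and it is used here only to explain origin. It shows essentially the footnote's wording as the former body text. The reason given for revising the body was "Clarification that patients with hypertension must monitor their blood pressure at home and keep a diary of the results". The footnote appears not to have been updated with it.

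**3. What scheduled clinic readings can show**

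Inputs are the visit days in Appendix A: Days 1, 8, 15 and 22 in Cycle 1, Days 1 and 15 in Cycles 2-3, and Day 1 of each 28-day cycle from Cycle 4. The visit window is ±3 days after Cycle 1.

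- Cycle 1: 8 − 1 = 7 days between readings.
- Cycles 2-3: 15 − 1 = 14 days, and 29 − 15 = 14 days to the next Day 1. With both windows used, the gap runs from 14 − 6 = 8 to 14 + 6 = 20 days.
- Cycle 4 onwards: 28 days. With both windows used, 28 − 6 = 22 to 28 + 6 = 34 days.

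Suppose a Grade 3 pressure is found at a visit and an antihypertensive is started or adjusted that day. The 7-day point then falls 14 − 7 = 7 days before the next scheduled reading in Cycles 2-3, and 28 − 7 = 21 days before it from Cycle 4. If the next reading is lower, the duration may have been under or over 7 days. If it is still Grade 3, the two readings do not show what happened between them. In Cycle 1 the weekly readings come close to the threshold.

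This applies to Grade 3 defined by pressure level. Table 11 also allows Grade 3 by intensity of treatment, which needs no reading.

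**4. Size**

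Table 3 gives hypertension in 55.4% of treated patients. The documents do not say how many cases were new on treatment, or how many patients will enter with an antihypertensive history. The number affected by the mismatch therefore cannot be calculated.

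**The case against.** The strongest case is that the footnote is shorter than Section 6.3.1 but does not conflict with it. It does not restrict monitoring to the group it names and exempts nobody. It agrees on timing, and a site that reads both can comply with both. Section 6.3.1 remains binding protocol text.

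The duration rule is also less exposed than it looks. It applies once an antihypertensive has been used or adjusted, so the patient is already under active management. For Grades 2 and 3, Table 11 refers to Appendix I, whose reprinted guideline summary encourages self-monitoring and review of home readings. Nothing prevents an interim check, and SAP Section 5.3 allows unscheduled measurements to count towards worst values.

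No planned analysis uses the diary. Vital signs are summarised by visit (SAP Section 17.6), hypertension as an event of special interest comes from coded adverse events (SAP Section 17.2.6), and no hypothesis is tested (SAP Section 5.5).

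Most of this stands and limits the consequence. It does not remove the mismatch. Appendix I offers guidance, and a site that relies on it and on interim checks is using discretion where Section 6.3.1 states a requirement. A site has to find Section 6.3.1 unprompted to know that the requirement exists.

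**Conclusion.** The inconsistency is real, lies between current passages, and should be corrected. A site following the schedule could omit daily home readings and the diary in patients who become hypertensive on study. Scheduled clinic readings alone cannot then settle the 7-day question in Table 11 from Cycle 2 onwards. This assumes that some sites work from the schedule without also applying Section 6.3.1, and that they add no interim readings. The documents neither confirm nor exclude that.

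A reader might infer more, and four stronger readings are not supported.

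- *On-drug hypertension would be missed.* Blood pressure is taken in every patient at every scheduled treatment visit. What could be missed is the home record.
- *Grading of hypertension would become site-dependent.* Table 11 grades by pressure, symptoms or treatment intensity. The 7-day duration governs the dosing action and not the grade.
- *Hypertension is the most frequent identified risk.* It has the highest percentage printed in Table 3, but the table gives none for hand-foot syndrome (PPE) or rash, both listed as very common.
- *About 64 expansion patients, 19 of them at Grade 3, would be affected* (0.554 × 116 = 64; 0.16 × 116 = 19, using Table 3 and Appendix I). These count all projected hypertension, including patients whom footnote 6 already covers for timing, and leave out the 12 escalation patients. They do not measure the effect of the mismatch.

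**What to change.** Reconcile Appendix A footnote 6, its copy in SAP Appendix 1, and Section 6.3.1 so that all three name the same patients, frequency and method of recording. Alternatively, footnote 6 could simply refer to Section 6.3.1, as footnote 7 does to Section 6.3.2, once the content of that section is confirmed. Which patients are monitored, and how, is for the sponsor's clinical team to decide; no monitoring rule is proposed here.

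The cost is a wording change in the protocol or a clarification letter to sites, with the same edit in the SAP reprint. No analysis changes. Keeping what Section 6.3.1 already requires would add no new procedure.
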